11.1.2 Severity

The following definitions will be used to rate the severity for any adverse event being collected as an endpoint/data point in the study and for all serious adverse events.

Mild: The adverse event is transient and easily tolerated by the patient.

Moderate: The adverse event causes the patient discomfort and interrupts the patient's usual activities.

Severe: The adverse event causes considerable interference with the patient's usual activities and may be incapacitating or life threatening.

11.1.3 Relationship to Pharmaceutical Product

The following definitions will be used to assess the relationship of the adverse event to the use of product:

Reasonable Possibility An adverse event where there is evidence to suggest a causal relationship between the product and the adverse event.

No Reasonable Possibility An adverse event where there is no evidence to suggest a causal relationship between the product and the adverse event.

If no reasonable possibility of being related to product is given, an alternate etiology must be provided for the adverse event.

11.1.4 Adverse Event Collection Period

Non-serious adverse events and serious adverse events will be reported to AbbVie from the time the physician obtains the patient's authorization to use and disclose information (or the patient's informed consent) until 30 days following the intake of the last dose of physician-prescribed treatment.

[figure not shown]
11.1.5**Serious and Non-serious Adverse Event Reporting**

In the event of an **SAE**, the physician will:

- For events from patients using the ABBVIE REGIMEN report to AbbVie within 24 hours of the physician becoming aware of the event by using the eCRF system or notifying the AbbVie contact representatives identified below.

In the event of a **non-serious AE**, the physician will:

- For events from patients using the ABBVIE REGIMEN report to AbbVie by using the eCRF system.

Primary contact for SAEs, AEs reporting:**Back-up contact for SAEs, AEs reporting:****11.1.6****Pregnancy Reporting**

Patients and their partners should avoid pregnancy and males should avoid sperm donation throughout the course of the HCV treatment and for 30 days after the end of treatment with DAAs.

In the event of a pregnancy occurrence in the patient, the physician will report to AbbVie within 24 hours of the physician becoming aware of the pregnancy by using the eCRF system or notifying the AbbVie contact person identified in Section 11.1.5.

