Enrollment will start in March 2017 and continue approximately 6 months and ABBVIE REGIMEN therapy will be administered according to physician's prescription and the local label to all enrolled subjects. All visits of the program will be organized according to routine clinical practice over 12 weeks of treatment period as well as 12 weeks follow-up period to assess the SVR12. All enrolled patients will be followed by a personal or telephone contact at 30 days after their last dose in the study.

9.5**Investigator selection criteria**

In order to assure credibility of the final results the below listed criteria will be considered during the recruitment process of physician/investigators:

- Physician licensed in infection diseases or gastroenterology;
- Physician is working at a national or regional hospitals or outpatient centers;
- Availability of patient population fulfilling the inclusion/exclusion criteria;
- Ability to appropriately conduct the observational program.

9.6**Inclusion Criteria**

ABBVIE REGIMEN will be prescribed by physicians according to the routine clinical practice. Patient can be included in the study if he/she will satisfy the following criteria:

1. Age \geq 18
2. Treatment-naïve or IFN/RBV-experienced adult male or female patients with confirmed CHC Gt1b and compensated liver cirrhosis, receiving therapy with the interferon-free ABBVIE 3D REGIMEN initiated not earlier than 2 weeks before the enrollment or the initiation is planned not later than 2 weeks after the day of enrollment in accordance to standard of care and in line with the current local label.
3. Patients must voluntarily sign and the Authorization (Consent) for Use/Disclosure of Data form prior to inclusion into the study.
4. Patient must not be participating or intending to participate in a concurrent interventional therapeutic trial.

9.7**Exclusion Criteria**

A patient will not be eligible for this PMOS if he/she fulfils the following criteria:

1. Co-administration RBV with the ABBVIE REGIMEN
2. Patients with Child Pugh B and C cirrhosis
3. Patients with a history of prior DAA therapy
4. Any other contraindications to the administration of ABBVIE REGIMEN according to the label

9.8**Description of Activities**

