The patient visits will be scheduled based on routine clinical practice and prescription of consulting physician. Prescription of ABBVIE REGIMEN is clearly separated from the decision to include the patient in the study. However, it would be included at least two observational visits (Visit 1 and EoT) plus one 30 days safety follow-up visit and one 12 weeks follow-up visit (SVR12) after the last dose of ABBVIE REGIMEN. Additional observational visits between Visit 1 and EoT can be done in case of clinical necessity and physician decision.

Information for patients enrolled within 2 weeks after initiation of ABBVIE REGIMEN is collected at routine patient visits therefore baseline patient data should be taken from medical records.

In total, there will be at least four study visits. Please refer to Table 2 for observational documentation.

Table 2. Program Activities

Assessment/ Procedure (only available data to be collected; no diagnostic or monitoring procedures to be applied to the patients apart from those of routine clinical practice)	Visit 1	Treatment Period (on-treatment visits)	Post-treatment (PT) Period	
			Safety Follow-up Visit ^c	SVR 12 Follow-up Visit
Authorization (Consent) for Use/Disclosure of Data form	X ^a			
Inclusion/Exclusion Criteria	X			
Demographic information	X			
IL28B	X			
Relevant CHC disease characteristics	X			
Liver fibrosis stage	X			
CHC treatment history	X			
HCV genotype and subtype	X			
HCV RNA samples	X	X		X
Clinical chemistry and hematology	X	X		X
ABBVIE REGIMEN initiation documentation	X			
ABBVIE REGIMEN adherence		X		
Concomitant medication	X	X		X
Relevant medical history, co-morbidities	X			
SAE, non-serious AE and pregnancy reporting	X	X	X	X

Abbreviations: EoT = End of Treatment (at Week 12 or at premature discontinuation),

PT = Post-Treatment

a Written patient authorization or informed consent must be obtained before any data documentation in the eCRF

b Patients who prematurely discontinue should return to the site to document EoT data

c Tolerability documentation until PT week 4, visit can be done as telephone call contact

Collected data and planned activities within the observational program:

Visit 1

- Signing of the Authorization (Consent) for Use/Disclosure of Data form by patient
- Assignment of patient's identification number (two-digit center number + two-digit patient individual enrollment number)
- Inclusion/exclusion criteria verification
- Demographics (sex, age, race)

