10.2 Adverse events

Only treatment-emergent adverse events will be analyzed.

Treatment-emergent AE is any reported event that begins or worsens in severity after initiation of study drug through 30 days post-study drug dosing.

All analyzed AEs will be coded using the MedDRA version 20.0 (or further updating) and tabulated in the report with grouping by primary system organ class (SOC) and preferred term (PT).

The frequency of a specific AE occurrence will be presented by the proportion of patients with this AE emergence as well as the total number of episodes this AE for a diagnosis.

The following tables with descriptive statistics in accordance with section 7.1 will be presented:

- all AE / SAE;
- AE / SAE by severity;
- AE / SAE by relationship to the study drug.

Tables of AE/SAE by severity (relationship to the study drug) will be prepared using the following rules. Each SOC / PT category will include only the AEs with the highest severity (relationship to the drug) in each patient, while in the Total category all AEs of this patient will be considered. At the same time, each patient will be counted only once with highest severity (relationship to the study drug) in each SOC and each PT level as well as Total level.

Also all AEs will be presented in listings. Additional listings for unintended medication errors will be provided.

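### Adverse events need only be reported from consent, but treatment-emergent events are counted from first dose, so early events in patients who enrol after starting treatment can be under-counted

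*Protocol*

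**What the plan says.** **Collection.** Protocol 11.1.4: "Non-serious adverse events and serious adverse events will be reported to AbbVie from the time the physician obtains" the patient's authorization or consent, and "until 30 days following the intake of the last dose of physician-prescribed treatment".

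**Enrolment.** Protocol 9.6 admits patients whose therapy was "initiated not earlier than 2 weeks before the enrollment or the initiation is planned not later than 2 weeks after the day of enrollment". The same section requires the signed "Authorization (Consent) for Use/Disclosure of Data form prior to inclusion into the study". A patient already on treatment can therefore consent up to 14 days after first dose.

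**Analysis.** SAP 10.2: "Treatment-emergent AE is any reported event that begins or worsens in severity after initiation of study drug through 30 days post-study drug dosing". Protocol 9.13.8 uses the same definition. SAP section 5 numbers study days from the start of treatment. The denominator is the safety population, meaning everyone with at least one dose.

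**Look-back.** For patients enrolled after starting treatment, Protocol 9.8 says that "baseline patient data should be taken from medical records". Protocol 9.8.2 documents concomitant medication from the first dose. No section gives the same instruction for adverse events.

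**The concern.** The numerator and denominator cover the interval from first dose to 30 days after the last dose. Required reporting covers only the part of that interval after consent. In a patient enrolled late, days that nobody was obliged to document are treated as fully observed and free of events.

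The error can go only one way, because events can be missed but not added. Describing tolerability is a secondary objective (Protocol 8.2.2), and adverse events are a listed secondary variable (9.9.2). The planned adverse event tables (SAP Tables 3.2.1 to 3.2.6) give one pooled column, so their reader could not tell how far late enrolment had lowered the percentages. Protocol 9.15 does not list this among the limitations.

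**Working it through.** The plan states no expected adverse event rate and no sample-size calculation, so there is no figure to reproduce. The check compares the two windows and then illustrates the size.

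**1. Windows for a patient who consents *d* days after first dose (*d* at most 14, Protocol 9.6)**

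- Counting window: 84 days of treatment + 30 days = 114 days.
- Outside required collection: at most 14/114 = 12.3% of the counting window, or 14/84 = 16.7% of treatment.
- If late consent is spread evenly over the 14 days, the average gap is 7 days: 7/114 = 6.1%.
- For a patient who consents on or before first dose, the gap is 0.

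**2. Illustration of the bias**

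Reported incidence = *R* × (1 − *q* × *e* × *m*), where:

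- *R* = true incidence, 22% (fatigue in the 60-patient trial described in Protocol section 7.0)
- *q* = share of patients who consent after first dose (not in the documents; 25% and 50% shown)
- *e* = share of first onsets that fall in the first 14 days (assumed: 12%, close to 14/114 under a constant rate, up to 50%)
- *m* = share of those early onsets that precede consent and go unreported (0.5 for evenly spread consent)

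| *q* | *e* | Calculation | Reported | Patients lost per 60 |
|---|---|---|---|---|
| 25% | 12% | 22 × (1 − 0.25 × 0.12 × 0.5) | 21.67% | 0.2 |
| 25% | 50% | 22 × (1 − 0.25 × 0.50 × 0.5) | 20.63% | 0.8 |
| 50% | 12% | 22 × (1 − 0.50 × 0.12 × 0.5) | 21.34% | 0.4 |
| 50% | 50% | 22 × (1 − 0.50 × 0.50 × 0.5) | 19.25% | 1.65 |

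The last column is (22% − reported) × 60.

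**3. Cross-check with a different model**

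Take an exponential time to first event over 114 days, with the hazard in days 1 to 14 equal to *k* times the later hazard and late patients all consenting at day 7. With *H* = −ln(1 − 0.22) and *h* = *H*/(14*k* + 100), the reported incidence in late patients is 1 − exp(−(*H* − 7*kh*)).

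| Share late | *k* = 1 | *k* = 3 | *k* = 5 |
|---|---|---|---|
| 25% | 21.7% | 21.3% | 21.0% |
| 50% | 21.4% | 20.5% | 20.0% |

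The direction is the same and the values lie in a similar range.

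**4. Does another section close the gap?**

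- The activities table in Protocol 9.8 ticks adverse event reporting at Visit 1, but the itemised Visit 1 list has no adverse event entry and sets no look-back.
- Protocol 9.13.8 says all events in included patients are to be reported but gives no start date, so it does not displace the specific rule in 11.1.4.
- The missing-date rule in SAP 7.3 classifies events that were reported. It cannot recover events that were not.

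**The case against.** The strongest reply is that 11.1.4 says when reporting starts, not that an event must begin after consent. Adverse events are ticked at Visit 1, and the data sources in Protocol 9.10 include charts and hospital records. The footnote to SAP Table 3.2.1 excludes only events before first intake, so an event between first dose and consent that a site did enter would be counted. This stands. A reader might infer that every pre-consent event is lost, and the documents do not support that. What need not be recorded is an event that resolved before consent. Events ongoing at consent may be entered, and those that worsen afterwards fall within the definition.

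Second, the bias depends on late enrolment, and 9.6 equally permits enrolment up to 2 weeks before first dose, where coverage is complete. This also stands, and the size is conditional on a share that the documents do not give.

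Third, the effect may be small beside the imprecision: the exact 95% interval for 13/60 is 12.1% to 34.2%. That bears on priority, but sampling error does not offset an error in one direction.

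Fourth, late enrolment could be worked out from the planned listings and study days. That is true, but the tables would still present pooled percentages without comment.

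**Conclusion.** The mismatch is real and one-directional. Following 11.1.4 as written allows events that began and resolved before consent to go unrecorded in late enrollees, while those patients count in full in the denominator. With a true incidence of 22%, evenly spread late consent and 12% to 50% of onsets in the first 14 days, the reported figure is about 21.7% to 20.6% if a quarter enrol late and 21.3% to 19.25% if half do. For those inputs the losses are upper bounds, because they treat every pre-consent onset as unreported. If nobody enrols late, there is no bias.

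Two stronger readings are not supported:

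- **A halving of reported incidence.** 22% becomes 11.0% only if every patient enrols late, all at day 14, half of all onsets fall in the first 14 days, and every one of those is lost. Nothing in the documents supports that combination.
- **A demonstrable selection of early stoppers.** Because 9.6 requires patients to be receiving or about to start therapy, a reader might infer that very early stoppers are under-represented, and that SVR12 in patients consented before first dose would show it. The selection is plausible but cannot be sized. SVR12 in the core population could not reveal it, because SAP section 6 excludes patients whose treatment ended on or before study day 55. In the target population, a subset of 30 (assumed) with 30/30 responders would still have an exact lower limit of 88.4%.

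**What to change.** 1. **Protocol 11.1.4:** state that, for patients enrolled after first dose, adverse events with onset between first dose and consent are transcribed from the medical record at Visit 1 and flagged as pre-consent. This matches the first-dose start already used for concomitant medication in 9.8.2.
2. **SAP 10.2:** report how many patients consented on or before first dose and how many after. Add a treatment-emergent column for the first group beside the pooled one, and state the limitation.

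The second change appears to need no new data. The treatment start date is named in SAP section 5, and the footnote to SAP Table 1.4.1 already uses the date of signing the authorization form. It can therefore be made even if collection can no longer be changed.

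The cost is one sentence in the protocol, some record review for late enrollees, and one extra table column with a smaller N and so wider uncertainty. Events taken from records may also be less complete than those collected prospectively, which is the reason for the flag.

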11.2 Product Complaint

11.2.1 Definition

A Product Complaint is any Complaint (see Section 11.0 for the definition) related to the biologic or drug component of the product.

For a product this may include, but is not limited to, damaged/broken product or packaging, product appearance whose color/markings do not match the labeling, labeling discrepancies/inadequacies in the labeling/instructions (example: printing illegible), missing components/product, or packaging issues.

Any information available to help in the determination of causality to the events outlined directly above should be captured.

11.2.2 Reporting

[figure not shown]
Product Complaints concerning the investigational product must be reported to the Sponsor within 24 hours of the study site's knowledge of the event via local Product Complaint reporting practices. Product Complaints occurring during the study will be followed-up to a satisfactory conclusion. All follow-up information is to be reported to the Sponsor (or an authorized representative) and documented in source as required by the Sponsor. Product Complaints associated with adverse events will be reported in the study summary. All other complaints will be monitored on an ongoing basis.

| Product complaints involving a non-Sponsor investigational product should be reported to the identified contact or manufacturer, as necessary per local regulations.

Product Complaints may require return of the product with the alleged complaint condition. In instances where a return is requested, every effort should be made by the investigator to return the product within 30 days. If returns cannot be accommodated within 30 days, the site will need to provide justification and an estimated date of return.

The description of the complaint is important for AbbVie in order to enable AbbVie to investigate and determine if any corrective actions are required.

Primary contact for Product Complaint reporting:

Back-up contact for Product Complaint reporting:

12.0 **Plans for Disseminating and Communicating Study Results**

At the end of this observational study, a report will be written by AbbVie or a CRO working on behalf of AbbVie. The required standard study report template will be followed. This report will contain a description of the objectives of the study, the methodology and its results and conclusions. The completed eCRFs, patient questionnaires, the final study output and study report are the confidential property of AbbVie and may not be released to unauthorized people in any form (publications or presentations) without express written approval from AbbVie. The study results will be submitted to local authorities by the participating countries per local laws and regulations.

The results of this study will be made publicly available on one of the primary registries in the World Health Organization (WHO) Registry Network which meet the requirements of the ICMJE (International Committee of Medical Journal Editors) and through scientific publications. Authorship will be in line with ICMJE' authorship requirements 7.

Data MATRIX

SF_STAT001_ver 2_Eng
Approval Date 18 July 2017

PI6-253 (CITRIN) _ STATISTICAL ANALYSIS PLAN _ FINAL 2.0 _ 16 Mar 2018

Protocol Number: PI6-253 (CITRIN)

Protocol Title: Real world evidence study of the effectiveness of Paritaprevir/r –
Ombitasvir + Dasabuvir without Ribavirin in patients with chronic HCV
G1b infection and compensated liver cirrhosis in the Russian Federation
– an observational, multi-center study

SAP version: Final 2.0

Effective date: 19 Mar 2018

REVISION HISTORY

| Nº | Version | Date | Changes |
|----|---------|------------|---|
| 1 | 1.0 | 16.08.2017 | New Document 
1) section 9 and corresponding tables shells was updated.– additionally to efficiency endpoints the following virologic outcomes were added to the analysis: breakthrough, failure to suppress and premature study drug discontinuation with no on-treatment virologic failure;– due to the fact that in the Russian clinical practice tests for HCV RNA often have limit of detection higher than 50 IU/mL and may vary across laboratories, the definitions for effectiveness outcomes were adjusted;– additional frequency tables for patients in subgroup without missing SVR12 data category were added;– method of 95% confidence interval calculation for odds ratio in logistic regression analysis was specified; |
| 2 | 2.0 | 16.03.2018 | 
2) the information about time windows for clinical laboratory data was moved to section 4.1 “General study design and plan”;3) tables shells for demographics and baseline characteristics was changed: one table was divided into several tables;4) list of tables, figures and listings was added. |

P16-253 (CITRIN) _ STATISTICAL ANALYSIS PLAN _ FINAL 2.0 _ 16 Mar 2018

TABLE OF CONTENTS

| | | |
|------|--|------------------------------|
| 1 | Abbreviations and definitions | 4 |
| 2 | Introduction | 5 |
| 3 | Study objectives and variables | 5 |
| 3.1 | Study objectives | 5 |
| 3.2 | Variables | 6 |
| 4 | Study design | 6 |
| 4.1 | General study design and plan | 6 |
| 4.2 | Sample size | 7 |
| 4.3 | Randomization and blinding | 8 |
| 4.4 | Planned analyses | 7 |
| 5 | General considerations | 8 |
| 5.1 | Reference start date/time, study day, baseline | Error! Bookmark not defined. |
| 5.2 | Windowing conventions | Error! Bookmark not defined. |
| 6 | Analysis populations | 8 |
| 7 | Statistical considerations | 9 |
| 7.1 | Standard descriptive statistics | 9 |

This document describes the planned data statistical analysis of an observational, multicenter, real world evidence study of the effectiveness of Paritaprevir/r – Omibitasvir + Dasabuvir without Ribavirin in patients with chronic HCV Gt1b infection and compensated liver cirrhosis in the Russian Federation (CITRIN).

This SAP is written according to ICH E9 Guideline [1] and Data MATRIX LLC SOP [2] using the Protocol Final version 1.0 dated 29 Nov 2016 and CRF Final version 1.1 dated 16 Mar 2017.

The purpose of this document is to provide a more technical and detailed elaboration of the principal features of the analysis, described in the Protocol, and to include detailed procedures for executing the statistical analysis.

The SAP needs to be finalized and signed prior to database soft lock. Revisions to the approved SAP may be made prior to database soft lock. In case of deviation from the finalized SAP, explanation will be provided in the clinical study report (CSR).

3 Study objectives and variables¹

3.1 Study objectives

The research question of this study is what is the effectiveness of the interferon-free 3DAA ABBVIE REGIMEN without RBV in patients with HCV Gt1b infection and compensated liver cirrhosis in a real life setting?

The Protocol defines the following *primary objective* of this study:

- to describe the effectiveness of the interferon-free 3DAA ABBVIE REGIMEN without RBV in patients with HCV Gt1b infection and compensated liver cirrhosis as evidenced by sustained virological response at 12 weeks after the end of treatment in routine clinical practice.

The Protocol defines the following *secondary objectives* of this study:

- to describe the EoT response rate;
- to assess the rate of relapse (timeframe for assessing relapse - between EoT and SVR 12);
- to describe baseline characteristics of patients with HCV Gt1b and compensated cirrhosis treated with AbbVie 3D regimen;
- to collect information on co-morbidities and concomitant medications in cirrhotic patients in the Russian population;
- to describe the tolerability of the ABBVIE REGIMEN.

¹ This section is based on the sections 8 “Research Question and Objectives”, 9.9 “Variables”, 9.13.4 “Primary Effectiveness Endpoints” and 9.13.5 “Secondary Effectiveness Endpoints” of clinical study Protocol.

P16-253 (CITRIN) _ STATISTICAL ANALYSIS PLAN _ FINAL 2.0 _ 16 Mar 2018

